
intervention effects vary among subgroups. Those with significant interactions ($p < .15$) will be considered as candidates for identifying subpopulations.

Cost

We will calculate the incremental cost per quit of the interventions over the 6-month follow-up period as follows: (total per-person costs of LCS-tailored intervention – total per-person costs of the lowest intensity comparator)/(cessation rate with the LCS-tailored intervention – cessation rate with the lowest intensity comparator).⁹⁶ From these comparisons, we will also be able to construct a “league table” comparing the relative cost-effectiveness of different intervention components.⁹⁷ While the study is specifically powered to detect differences across factorial dimensions, we will develop incremental cost per quit estimates for all intervention comparisons that are proven effective, whether it be for individual factorial dimensions’ main effects (counseling duration, NRT duration, or systematic referral), for specific permutations of the intervention components versus usual care or for intervention permutations versus each other. Costs of implementation included in our analyses will be: 1) personnel time related to intervention delivery (training, minutes of counseling, contact attempts, maintaining data and information systems), 2) NRT costs (medication, delivery), and 3) systematic referral to community resources. While systematic referral is free in Boston, access to similar services elsewhere in the country may not be, so this will be an element of our sensitivity analyses. We will also include patient time as an indirect cost. The TTS database will document all implementation costs. All intervention costs incurred will be included in the analysis, even for patients who do not complete their intervention course. Research costs will be excluded. The denominator for the cost analyses will be based on the primary outcome. Uncertainty in cost and effectiveness inputs will be incorporated into the incremental cost per quit comparisons using Monte Carlo methods allowing us to determine whether these ratios are significantly different from zero. The robustness of the cost-effectiveness ratio estimates will be further examined in sensitivity analyses in which each parameter is varied, singly and in combination, through plausible ranges. Sensitivity analyses will also consider how cost-effectiveness changes based on payment arrangements and stakeholder (provider, payer, and patient) perspectives to identify where incentives to adopt the interventions differ. For example, overhead costs such as counseling training and data/information systems are borne by the provider, and indirect costs are borne by patients, but treatment costs (counseling, NRT) and the cost of systematic referral-style resources may be borne by providers, payers, and/or patients (e.g., copayments). Assessing how assignment of costs to different stakeholders changes cost-effectiveness from different perspectives will be critical to understanding how to scale up the intervention to other LDCT screening settings and what payment policies will produce the best public health outcomes.

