
Sample size/ Power calculations

Power calculations are based on our primary analysis, which is to assess the effect of each intervention component (e.g., shorter counseling vs. longer counseling) on our primary outcome, 7-day point-prevalence tobacco abstinence at 6-month follow-up. This is a two-sample comparison between patients that receive one intervention component (e.g., longer counseling) and those that receive the other (e.g., shorter counseling). We conservatively estimate that 160 patients/month will have LCS, of whom 50% will be current smokers. Assuming a 50% enrollment rate, we aim to recruit a total N of 720 patients. This sample size allows us to allocate N=360 to each treatment component comparison (main effect). Our

Reference rate	Relative Risk		
	1.4	1.45	1.5
16%	0.71	0.80	0.87
17%	0.74	0.83	0.90
18%	0.77	0.86	0.92
19%	0.80	0.88	0.93
20%	0.83	0.90	0.95
21%	0.85	0.92	0.96
22%	0.87	0.93	0.97

outcome of interest will also be assessed at 3-month followup, which allows us to use a longitudinal generalized estimating equations approach wherein power is proportional to the within-person correlation. We estimate the correlation between 3 month and 6 month smoking cessation to be 0.6. Assuming N=360 patients in each condition, a Type 1 error rate of 0.05, a 25% attrition rate by 6 month follow-up, and a 15% cessation rate for the reference group, we will have 92.3% power to detect a risk ratio of 1.6 (15% vs. 21%). Under those same conditions, but with a 10% cessation rate for the reference group, we will have 79.0% power to detect a risk ratio of 1.6 (10% vs. 16%). Given that this is full factorial design, we will have the same power to detect two-way interactions between components. Further, we will also have 77.9% power to detect a risk ratio of 2.0 in the difference between our most intensive set of treatments (longer counseling, longer NRT, and community support; N=90) and our least intensive set of treatments (shorter counseling, shorter NRT, and no community support; N=90) after six months, assuming a 15% reference rate and 25% attrition.

Reduction from initial power calculations

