This study was initially powered conservatively to detect a smaller risk ratio of 1.4 and did not account for additional power provided through within-person correlation via repeated measurement of our outcome of interest. Initial power calculations, assuming a Type 1 error rate of 0.05, 25% attrition at 6 months, and no within-person correlation showed that our original N of 960 patients (N=480 per condition) gave us 85.0% power to detect a risk ratio of 1.4 with a reference rate of 15%. Updated power calculations accounting for within-person correlation of 0.6 show that this original N gives us 96.8% power to detect our target risk ratio of 1.6, assuming 25% attrition at 6 months and a 15% reference cessation rate.

Our previous power calculation assumed a 25% attrition rate at 6 months. We re-examined this assumption after halfway through the recruitment. Our new estimates are 12.7% attrition rate at 3 months and 15.9% attrition rate at 6 months. Based on these estimates, we further reduce the target recruitment from 720 to 640. Combining data from both 3-month (estimated N=559) and 6-month (estimated N=539) assessments, the effective sample size will be 768 after taking into account of within-person correlation using a conservative estimate of 0.6. The new sample size will have 70% power to detect a risk ratio of 1.6 (10% vs. 16%) and 81% power to detect a risk ratio of 1.7 (10% vs. 17%).

VII.. RISKS AND DISCOMFORTS (Stratify by common and uncommon)

Prior to enrollment, potential patients will be cautioned about the potential negative psychological and physical implications of joining the study and/or quitting smoking.

Psychological Risks

Individuals may find it stressful to answer questions and discuss their smoking behaviors. The risks associated with these discussions are minimal, especially when compared to the benefits of smoking cessation.

The potential risks to subjects include: 1) speaking with a counselor about smoking and/or cancer-related topics has the potential for increasing psychological vulnerability; 2) experiencing physical and emotional withdrawal symptoms from smoking cessation; and 3) potential side effects of using nicotine replacement therapy.

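### The planned test of whether cost-per-quit ratios differ from zero carries almost no information on value for money

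*Combined protocol and SAP*

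**What the plan says.** The Cost section defines the ratio as the difference in per-person cost divided by the difference in cessation rate, against the lowest-intensity comparator. On the effectiveness side, "The denominator for the cost analyses will be based on the primary outcome", that is, 7-day abstinence at 6 months.

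On uncertainty: "Uncertainty in cost and effectiveness inputs will be incorporated into the incremental cost per quit comparisons using Monte Carlo methods". The stated purpose of this step is a significance test of each ratio, described as "allowing us to determine whether these ratios are significantly different from zero".

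On which ratios are produced: "we will develop incremental cost per quit estimates for all intervention comparisons that are proven effective". This covers the three main effects and also extends to estimates "for specific permutations of the intervention components versus usual care or for intervention permutations versus each other". The condition that a comparison be proven effective is not defined.

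The section also plans a league table, sensitivity analyses on single and combined parameters, and provider, payer and patient perspectives. It notes that the referral service carries no charge locally, although it may elsewhere. It gives no cost figures, value per quit, net-benefit measure, acceptability curve, or rule for a zero or negative denominator.

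**The concern.** A finite ratio of cost difference to quit difference is zero only if the cost difference is zero. Four extra counseling sessions, or eight rather than two weeks of free patches, can be expected to cost more wherever the extra is used. For those components, rejecting zero does not show whether a quit was bought at a reasonable price.

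Referral has the opposite problem. If its added cost is close to zero, the ratio is close to zero however many quits it produces. An effective and cheap component could then be reported as not significant.

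A ratio is also awkward to summarize when its denominator can change sign. It passes through infinity, and a negative value can mean either cheaper and better or dearer and worse. Percentile limits taken across that break are hard to interpret.

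The section presents the stakeholder cost analysis as important for scale-up and payment policy. A test that does not respond to cost cannot inform either.

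**Working it through.** **Inputs from the documents.** Total N is 640 ("we further reduce the target recruitment from 720 to 640") in eight equal cells, so 320 vs 320 per main effect and 80 per cell. Patients lost to follow-up count as smokers, so all randomized patients stay in the denominator. The planned effect is 10% vs 16%. Alpha follows "a Type 1 error rate of 0.05"; sidedness is not stated and is taken as two-sided.

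**Assumptions.** The documents give no costs. Added cost per person is varied from $50 to $15,000, with per-person SD equal to the mean.

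**1. The plan's own power figures.** The Cost section states none. The sample-size section gives 70% (10% vs 16%) and 81% (10% vs 17%) at an effective N of 768, taken here as given, so 384 per group.
- 10% vs 16%: null SE = √(2 × 0.13 × 0.87 / 384) = 0.02427; alternative SE = √((0.09 + 0.1344) / 384) = 0.02417. z = (0.06 − 1.96 × 0.02427) / 0.02417 = 0.51, so power is 69.6%.
- 10% vs 17%: the same formula gives 81.1%.

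Both stated figures reproduce. With 320 per level and the 6-month outcome alone, which is the ratio's denominator, power at 10% vs 16% is 61.7%.

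**2. What the zero test reduces to.** The SE of the cost difference is mean × √(2/320) = 0.079 × mean, so the added cost lies about 12.6 SEs above zero and practically every cost draw is positive. Each ratio draw then has the sign of its quit-difference draw. The 2.5th percentile of the ratio is above zero exactly when fewer than 2.5% of quit-difference draws are negative. That is the quit-rate test again, and the size of the cost drops out.

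Simulation (2,000 trials per cost, 2,000 draws each, 320 per level, 10% vs 16%):

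| Assumed added cost | True cost per quit (cost / 0.06) | Ratio interval excludes zero | Quit difference significant | Excludes zero, given significant |
|---|---|---|---|---|
| $50 | $833 | 62.2% | 62.2% | 98.5% |
| $150 | $2,500 | 61.2% | 61.1% | 98.6% |
| $1,500 | $25,000 | 60.0% | 59.9% | 98.7% |
| $15,000 | $250,000 | 62.0% | 62.0% | 98.5% |

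The small differences between rows are simulation noise. A component costing $833 per quit and one costing $250,000 per quit pass equally often. With no true quit difference (10% vs 10%), the interval excludes zero in 4.6% to 6.0% of trials, about the usual type 1 error.

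**3. Near-free component.** If cost draws fall on both sides of zero while quit-difference draws are all positive, the ratio draws also fall on both sides of zero. The test then becomes a test of added cost, and a component that produces quits at almost no cost tends to fail it.

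**4. Zero or negative denominators at 10% vs 16%.** Normal approximation with half a patient's correction for ties, z = (0.06 − 0.5/n) / √((0.09 + 0.1344)/n):
- n = 320: z = 0.0584 / 0.0265 = 2.21, probability 1.4% (simulated 1.3% to 1.4%).
- n = 80: z = 0.0538 / 0.0530 = 1.01, probability 15.5% (simulated 15.3% to 15.5%).

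Range holding 95% of simulated ratios (200,000 draws), before any restriction to significant comparisons:

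| Assumed added cost | Main effect, 320 vs 320 | Single cells, 80 vs 80 |
|---|---|---|
| $50 | $413 to $3,830 | −$3,752 to $4,194 |
| $150 | $1,236 to $11,396 | −$11,275 to $12,628 |
| $300 | $2,470 to $22,866 | −$22,487 to $25,107 |

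**5. Effect of restricting to significant comparisons.** At $150, 320 per level and 10% vs 16%, the range narrows to $1,238 to $3,006. The median falls to $2,044 against a true $2,500: 1 − 2,044/2,500 = 18% too favorable. Without the restriction the median is $2,469.

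**The case against.** The strongest reply is that the section produces ratios only for comparisons proven effective. If that means statistically significant, most near-zero denominators never become ratios. This stands, and it largely removes the instability. It does not rescue the test, which about 98% to 99% of such comparisons then pass. It also introduces the 18% bias, and at the 62% significance rate above, roughly 38% of real effects of the planned size would get no cost-per-quit estimate.

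A reader might infer that main-effect ratios generally break down. At 10% vs 12%, about 23% of samples have a zero or negative quit difference. But that difference is a third of the planned one; at 10% vs 16% the figure is about 1%, and the unrestricted range is wholly positive.

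A reader might also say that every component costs more by design, so the zero null is always false. The documents do not support that for referral: the service is free locally and its price is a sensitivity parameter. Counselor time may still add some cost.

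Finally, the text never says that a significant ratio means cost-effective. The ratio estimates, sensitivity analyses and stakeholder perspectives would also be available. That is fair, but none of them supplies another inferential criterion.

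**Conclusion.** The concern holds. The zero test is the section's only inferential criterion. For longer counseling and longer NRT it duplicates the quit-rate test: about 62% of trials pass at 10% vs 16% across a 300-fold range of assumed cost. For referral, it could fail a good-value component if the added cost is near zero.

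Instability of the ratio is a secondary and conditional problem. It is small for main effects at the planned effect (about 1% of samples), material for single cells of 80 (about 15%), and largely absent if ratios are confined to significant comparisons, at the price of the 18% bias.

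The conclusion on the test needs only an added cost clearly above zero. The dollar ranges scale with the assumed cost and are illustrative.

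A reader might go on to infer that the league table would rank components wrongly. The documents do not show this: the table is built from the ratio comparisons rather than from the significance test, and no mis-ranking has been demonstrated. This is a supporting economic analysis; the primary outcome and its test are unaffected.

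**What to change.** - Delete the test of the ratios against zero.
- For all three main effects, whether or not significant, report incremental cost and incremental quits jointly, each with its interval.
- From the same Monte Carlo draws, report incremental net benefit (value per quit × quit difference − cost difference) with intervals, and acceptability curves, over a range of value per quit fixed before the analysis.
- Define what counts as proven effective for any permutation comparison still subject to that condition.

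This is a change of wording in the Cost section. It uses the inputs and draws already planned and needs no new data. The one added burden is choosing and justifying a range of value per quit, which the documents do not supply.

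### Several stated powers do not follow from their stated inputs: 92.3% is attached to 15% vs 21%, which is a risk ratio of 1.4, and the power table matches N=960, not 720 or 640

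*Combined protocol and SAP*

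**What the plan says.** All places are in section VI of the combined protocol and SAP.

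Sample size/Power calculations works at N=720: "This sample size allows us to allocate N=360 to each treatment component comparison (main effect"). It assumes a type 1 error rate of 0.05, 25% attrition by 6 months and a 3- to 6-month correlation of 0.6. It then makes four statements:
- for a 15% reference rate, "we will have 92.3% power to detect a risk ratio of 1.6 (15% vs. 21"%);
- for a 10% reference rate, "we will have 79.0% power to detect a risk ratio of 1.6 (10% vs. 16"%);
- on interactions, "Given that this is full factorial design, we will have the same power to detect two-way interactions between components";
- on the extreme cells, "we will also have 77.9% power to detect a risk ratio of 2.0 in the difference between our most intensive set of treatments" and the least intensive set, with 90 patients in each cell, a 15% reference rate and 25% attrition.

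A table of power for reference rates of 16–22% and risk ratios of 1.4, 1.45 and 1.5 sits in the same paragraph. No N is attached to it in the text.

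Reduction from initial power calculations gives the history from 960 (480 per condition) to 720, and then "we further reduce the target recruitment from 720 to 640". It revises attrition to 12.7% at 3 months and 15.9% at 6 months, says "the effective sample size will be 768 after taking into account of within-person correlation using a conservative estimate of 0.6", and concludes: "The new sample size will have 70% power to detect a risk ratio of 1.6 (10% vs. 16"%), with 81% for 10% vs 17%. It gives no new table, interaction power or extreme-cell power.

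**The concern.** The lead statement contradicts itself: the risk ratio and the pair of rates in the same clause cannot both be right. The table gives powers that neither the paragraph's own sample size nor the current target delivers. The extreme-cell figure seems not to use the attrition quoted with it. The interaction sentence names no effect size or scale.

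At stake is what a reader believes the trial can show. Taken at its printed rates, the first statement promises over 90% power for a 6-point difference. The interaction sentence matters because Outcomes/analysis makes interactions the secondary analysis and uses them to judge whether components work synergistically or antagonistically. Someone relying on equal power could give a non-significant interaction more weight than it can carry.

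**Working it through.** **Method.** Two-proportion test, pooled variance under the null, alpha 0.05, n per group, p̄ the mean of p1 and p2:

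Power = Φ{ [ |p2−p1|·√n − 1.96·√(2p̄(1−p̄)) ] / √( p1(1−p1) + p2(1−p2) ) }

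The plan does not state sidedness. Two-sided is assumed because the plan names chi-square tests and the next two checks fit it.

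**Step 1. The N=640 figures.** 768/2 = 384 per level. 10% vs 16% gives 0.696 and 10% vs 17% gives 0.811, so the plan's 70% and 81% are reproduced. One-sided they would be 0.797 and 0.885. The 768 is not derived. The expected numbers are 559 and 539, total 1,098. The usual conversion for two correlated measures is 1,098/(1+0.6) = 686, or 343 per level, which gives 0.647 and 0.766. A factor of 0.7 gives 1,098 × 0.7 ≈ 768, but the text names no such factor.

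**Step 2. The table.** Largest absolute error over the 21 cells:

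| n per group | Largest error | 16%, risk ratio 1.4 (printed 0.71) |
|---|---|---|
| 480 (N=960) | 0.004 | 0.71 |
| 360 (N=720) | 0.123 | 0.59 |
| 320 (N=640) | 0.172 | 0.54 |

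At 480 every cell agrees to rounding. The closest one-sided fit (n = 378) misses by up to 0.013, more than rounding allows.

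**Step 3. The 92.3% and 79.0%.** 21/15 = 1.4; 1.6 × 15% = 24%; 16/10 = 1.6. The plan does not give 3-month attrition, the conversion for correlation, or whether dropouts counted as smokers stay in n, so a range is needed. Observations per level over two visits are 540 (25% lost at both), 630 (25% lost at 6 months only) or 720 (none removed). Each is divided by 1.6 or multiplied by 0.7.

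| Effective n per level | 15 vs 21 | 15 vs 24 | 10 vs 16 |
|---|---|---|---|
| 540/1.6 = 337.5 | 0.528 | 0.841 | 0.640 |
| 540 × 0.7 = 378 | 0.574 | 0.879 | 0.690 |
| 630/1.6 = 394 | 0.592 | 0.892 | 0.707 |
| 630 × 0.7 = 441 | 0.641 | 0.923 | 0.756 |
| 720/1.6 = 450 | 0.649 | 0.927 | 0.764 |
| 720 × 0.7 = 504 | 0.699 | 0.951 | 0.809 |

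For example, 15 vs 21 at 337.5: (0.06 × 18.37 − 1.96 × 0.5433)/0.5417 = 0.069, and Φ(0.069) = 0.528. To reach 0.923 for 15 vs 21 takes n = 937 (771 one-sided). Even 720 fully independent observations per level give only 0.843 (0.907 one-sided).

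The 79.0% for 10 vs 16 lies above the 64–76% found with attrition applied, and inside 76–81% only if attrition does not reduce n.

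**Step 4. The extreme cells, 15% vs 30%.** 90 = 720/8.
- Correlation gain only, no attrition: 90 × 2/1.6 = 112.5 gives 0.772 pooled, 0.779 by the arcsine formula.
- 25% loss at both visits: 84.4 gives 0.648.
- 6-month completers only: 67.5 gives 0.551.

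At N=640 there are 80 per cell: 67.3 six-month completers give 0.550, 80 gives 0.624, 686/8 = 85.8 gives 0.655, and 768/8 = 96 gives 0.705.

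**Step 5. Interactions.** In a balanced factorial, an effect-coded interaction coefficient has the same standard error as an effect-coded main effect. On the risk-difference scale, an equal coefficient means a difference of differences twice the main effect. Illustrative cell rates (assumed), Wald test, N=640 with both visits:
- 10/10/13/19%: main effect (13+19)/2 − (10+10)/2 = 6 points; difference of differences (19−13) − (10−10) = 6 points. At an effective total of 768, main effect 0.70 and interaction 0.24; at 686, 0.65 and 0.22. On the log-odds scale the same interaction has about 0.17 and 0.16.
- 10/10/10/22%: main effect 6 points, difference of differences 12. Both have 0.71 at 768 and 0.66 at 686.

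**The case against.** The strongest reply is that 21% is a misprint. The clause itself says 1.6, the next subsection again calls 1.6 the target risk ratio, and 15% vs 24% gives exactly 0.923 at 441 per level. That stands as the likely explanation, but it does not make the printed pair right. Nor does it settle the 79.0%, which is 0.756 at that same n.

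Second, the analysis plan counts patients lost to follow-up as smokers, so n may not shrink. That is fair and is why the range runs to 70%; it does not bring 15% vs 21% near 92.3%.

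Third, the cut to 640 is disclosed and new main-effect powers are given. That stands for main effects; the table and extreme-cell figure remain in current text without replacement. A caption giving the table's N may have been lost in conversion from PDF, so the missing label is not itself held against the plan. The mismatch with 360 and 320 remains.

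Some stronger readings are tempting but unsupported:
- **The trial is powered for a 6-point effect at a 15% base rate and falls far short.** The documents name 1.6, not 1.4, as the current target.
- **The interaction claim is simply false.** It is true for equal effect-coded coefficients; the fault is the unstated size and scale.
- **The 77.9% is left over from a larger sample.** Its 90 per cell is the paragraph's own 720/8. It is larger only than the 80 that N=640 gives, and unapplied attrition explains the figure.
- **A non-significant interaction will be read as no interaction.** No passage says so.

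**Conclusion.** Wrong as written. The contradiction between 1.6 and 15% vs 21% needs no assumption, and no choice of attrition, correlation or sidedness yields 92.3% for that pair. The table's match to N=960 is equally firm.

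The other parts depend on assumptions. That 92.3% belongs to 24% is an inference. The 79.0% and 77.9% cannot be reproduced with the stated attrition applied, on two-sided tests; one-sided, with neither attrition nor correlation, 15 vs 24, 10 vs 16 and the extreme cells give 92.1%, 77.4% and 78.2%, near the printed values but without two of the plan's own inputs. The 65% and 77% at N=640 assume the usual conversion for two correlated measures. The interaction powers depend on the chosen cell rates and scale.

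None of this shows that the sample size or primary test must change. It shows that several stated powers are higher than their inputs support, or cannot be checked from them.

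**What to change.** 1. Change the pair 15% vs 21% to 15% vs 24%. State sidedness, 3-month attrition, and whether dropouts counted as smokers stay in n. Recompute the 92.3% and 79.0% from those inputs without presupposing either value.
2. Recompute the table for N=640, or label it as belonging to N=960 and superseded.
3. Recompute the extreme-cell power for 80 per cell with the stated attrition applied.
4. Qualify the interaction sentence: power equals that of a main effect only for a difference of differences twice as large, on the risk-difference scale. For one equal to a 6-point main effect (N=640, both visits, illustrative cells above) it is about 22–24% on that scale and about 16–17% on the log-odds scale.
5. Show how 768 is obtained, and restate the 70% and 81% if it changes.

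The cost is recalculation and rewording. Sample size, primary test and the secondary status of interactions stay as they are; the only downside is less favourable stated powers.

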Proximal Outcomes/Mediators

All proximal outcomes/mediators will be assessed via survey at baseline and follow-up. Smoking beliefs. Readiness to quit (1 item 10-point 'contemplation ladder' ^{84,85}), importance and confidence to quit (1 item 10-point scales), 4 item perceived lung cancer risk, and 2 item perceived benefits of quitting.^{47,57} Health and screening beliefs. Self-reported overall health status (1 item from the SF-36 survey⁸⁶), 2 item perceived benefits of screening.^{47,57} Emotional symptoms. Anxiety and depression symptoms (PROMIS Anxiety and Depression 4a short-forms), worry about lung cancer (1 item about level^{87, 88}). Environmental factors. Living with a smoker in the household, 1 item 4-point scale about rules about smoking in the household⁸⁹, environmental workplace/hobby exposure and social support (PROMIS emotional and informational 4a short forms).⁸⁸

Analysis plan

All analyses will be intent-to-treat; we will classify patients who are lost to follow-up and those who do not provide a sample as current smokers.⁹² We will explore whether the mechanism of missing data is missing at random by comparing patient characteristics between those who complete follow-up vs. those who do not. We will perform sensitivity analysis: 1) limited to those who have complete data, and 2) multiple imputation for missing data.⁹³

Factorial design

In a factorial research design, two or more independent variables are concurrently examined within the same trial.^{94, 95} The three proposed factors will be crossed with one another to create a total of eight experimental conditions. An equal number of subjects will be randomly assigned to each condition, using a random number generator. This is not an 8-arm randomized controlled trial, but instead allows for an efficient examination of main effects for each variable over the entire sample of 640 subjects. This approach allows examination of three key treatment development questions in a much more time-efficient and economical manner by simultaneously performing three studies within the single trial. This achieves power to detect between-group differences that is equivalent to performing three separate randomized trials.⁹⁴

Outcomes/analysis

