Outcome measures will be assessed at baseline, 3-, and 6-months follow-up. At the outset, we will examine the frequency distributions of all variables. Data from all PHS sites will be pooled for analysis, after confirming there is no significant heterogeneity among sites or adjusting as needed. We will compare the baseline characteristics to assess whether randomization distributed covariates evenly. We will determine whether there is differential dropout in the groups and consider developing probability-of-completion weights to obtain unbiased estimates of treatment effect. The primary analysis will assess the effects of each intervention component in terms of its association with the **primary outcome** (cotinine-confirmed or self report of cessation at 6-months follow-up), **secondary smoking outcomes** and **proximal outcomes/mediators**: (a) short vs long counseling (conditions 1/2/5/6 vs. 3/4/7/8), (b) short vs long NRT (conditions 1/3/5/7 vs conditions 2/4/6/8), and (c) provision of systematic referral or not (conditions 1-4 vs. 5-8). Given the balanced complete factorial design,⁹⁴ each of the three main effect estimates will be based on the full sample size of 640. Cross-sectional analyses will be conducted for outcomes assessed at 3, and 6 months separately. For binary outcomes, chi-square tests will be used to compare the outcomes between groups for each follow-up time. For continuous outcomes two-sample t-tests or Wilcoxon rank sum tests, whichever more appropriate, will be used to compare between groups. A longitudinal analysis using Generalized Estimating Equations (GEE) techniques will also assess the overall impact of each component by including data from all follow-up time points. The secondary analysis will examine the interaction between components, which will provide insight into whether certain combinations of components are most useful. We will test the three-way and two-way interaction terms in the regression models. If there are component interactions, we will determine whether the components are synergistic or antagonistic. Exploratory analyses will examine the moderator effects on treatment effectiveness of the intervention components and groups. Of primary interest are sociodemographic characteristics (sex, race/SES, age), smoking characteristics (quit motivation, nicotine dependence), medical history, LCS-related factors (test results, and point of study entry), delivery modality selected (phone vs. video) and language of participation (English vs. Spanish). We will test the effects of these factors in multivariable logistic regression models to determine their association with the primary and secondary smoking outcomes. We will test for interactions between intervention and these factors to determine whether

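### The 85.0% power stated for the original 960-patient design is about 55% on its own inputs, and the 10% vs 16% powers given for N=720 and N=640 are also too high

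*Combined protocol and SAP*

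**What the plan says.** All figures are in section VI of the combined protocol and SAP, under Sample size/Power calculations and Reduction from initial power calculations.

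- **N=960.** The stated basis is "Initial power calculations, assuming a Type 1 error rate of 0.05, 25% attrition at 6 months, and no within-person correlation". The sample size at this stage is 960, or 480 on each side of a main-effect comparison. The plan claims that this "gave us 85.0% power to detect a risk ratio of 1.4 with a reference rate of 15" per cent. It presents this as a cautious starting point. With correlation 0.6 it adds that "this original N gives us 96.8% power to detect our target risk ratio of 1.6", again with 25% attrition at 6 months and a 15% reference rate.
- **N=720.** With 360 per level, 25% attrition by 6 months and correlation 0.6, the plan claims "79.0% power to detect a risk ratio of 1.6 (10% vs. 16" per cent).
- **N=640.** With 559 patients expected at 3 months and 539 at 6 months, the plan takes an effective sample size of 768 at correlation 0.6. From this it claims "70% power to detect a risk ratio of 1.6 (10% vs. 16" per cent) and 81% for 10% vs 17%.
- **Power table.** Rows run from a 16% to a 22% reference rate, and columns are risk ratios 1.4, 1.45 and 1.5. The 16% row reads 0.71, 0.80, 0.87. No sample size is printed.

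**The concern.** At a fixed risk ratio and sample size, power falls as the reference rate falls. A table that shows 0.71 for a risk ratio of 1.4 at 16% therefore sits badly with 85.0% at 15%, especially as the 85.0% is said to allow for 25% attrition. The 79.0% and 70% also look high for their stated inputs.

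The section uses these numbers to describe how much power was available at the start and how much remains after two reductions in sample size. A reader who has to interpret a null main effect will turn to it. Each of the figures at issue overstates power.

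**Working it through.** **Method.** The planned test is: "For binary outcomes, chi-square tests will be used to compare the outcomes between groups for each follow-up time". Allocation is equal ("An equal number of subjects will be randomly assigned to each condition"), so each main effect compares two halves. Sidedness is not stated; I take two-sided 0.05. With n analysed per level and p̄ the mean of p1 and p2:

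power = Φ{ [ |p2 − p1|·√n − 1.96·√(2p̄(1−p̄)) ] / √(p1(1−p1) + p2(1−p2)) }

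**1. Reproduce the table.** With n = 480 the 16% row computes to 0.712, 0.803, 0.874, against 0.71, 0.80, 0.87 printed. All 21 cells agree to within 0.005. So the table matches 480 analysed per level, which is the original allocation with no attrition. A 15% row at that n would read 0.68, 0.77, 0.85.

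**2. The 85.0% figure.** Here p1 = 0.15, p2 = 0.15 × 1.4 = 0.21, and n = 480 × 0.75 = 360.

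- √(2 × 0.18 × 0.82) = 0.5433; √(0.1275 + 0.1659) = 0.5417
- (0.06 × √360 − 1.96 × 0.5433)/0.5417 = (1.138 − 1.065)/0.5417 = 0.136; Φ = **55.4%**

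| Variant | Power |
|---|---|
| Other two-sided formulas (unpooled, arcsine, log scales, continuity correction), n = 360 | 51.5% to 55.6% |
| Lost patients counted as smokers: 480 per level, 11.25% vs 15.75% | 53.2% |
| No attrition, n = 480 | 67.8% |
| One-sided, n = 360 | 67.4% |
| One-sided, n = 480 | 78.1% |

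No variant reaches 85%. About 735 analysed per level would be needed. At n = 480 with no attrition, about 85% appears for a risk ratio of 1.5 at 15% (84.7%) or 1.4 at 21% (85.1%). Either could be the source; the document does not say.

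**3. The 79.0% figure (N=720, 10% vs 16%).** A patient seen at both visits counts as 2/(1 + 0.6) = 1.25 observations. The 3-month attrition at this stage is not given, so I show the range:

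- 25% already lost at 3 months: 270 × 1.25 = 337.5 per level, power 64.0%
- none lost at 3 months, total observations/1.6: (360 + 270)/1.6 = 393.75, power 70.7%
- none lost at 3 months, pairs plus singles: 270 × 1.25 + 90 = 427.5, power 74.2%

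The stated 79.0% is what 480 per level gives with no repeated measures (79.0%).

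**4. The 70% and 81% figures (N=640).** Given 768, or 384 per level, power is 69.6% and 81.1%, so both follow from 768. But 768 does not follow from its own inputs:

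- (559 + 539)/1.6 = 1,098/1.6 = 686
- 539 × 1.25 + 20 = 694, treating everyone seen at 6 months as also seen at 3 months
- correlation implied by 768: 1,098/768 − 1 = 0.43, not 0.6

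With 686 to 694 (343 to 347 per level), power is 64.7% to 65.2% for 10% vs 16% and 76.6% to 77.1% for 10% vs 17%.

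**5. The 96.8% figure (N=960, risk ratio 1.6).** A ratio of 1.6 at 15% means 24%. With attrition only by month 6, effective n is 360 × 1.25 + 120 = 570 per level and power is 97.0%. With 25% lost at both visits it is 360 × 1.25 = 450 and 92.7%.

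**The case against.** The best defence is that 85.0% describes an abandoned design. The cut to 720 rests on moving the target risk ratio to 1.6 and on using repeated measures; the cut to 640 rests on re-estimated attrition. Correcting 85.0% changes no current sample size or analysis, and the plan openly reports only 70% power at N=640. This stands as a limit on the consequence. It does not rescue the figure, which is reported in current text and fails on the inputs given beside it. The N=640 figures describe the present design.

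The table prints no sample size and has no 15% row, so tying it to 480 per level is inference. That is true, though agreement in 21 cells is strong support, and the 55% does not depend on the table.

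Three stronger readings are tempting, and the documents do not support them.

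- A reader might infer that 96.8% should be about 93%. That assumes the full 25% is lost by month 3, whereas the text places the attrition at 6 months. On that reading the figure reproduces.
- A reader might infer that 79.0% and 70% cannot both hold because the 6-month completers are almost equal (720 × 0.75 = 540 against 539). Both are repeated-measures powers, so 3-month data count, and equal 6-month numbers do not force equal power. Each figure fails for its own reason.
- A reader might infer that 70% and 81% are miscalculated powers. They follow correctly from 768; the fault is in the 768.

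**Conclusion.** The concern holds for specific figures, not for the section as a whole. The 85.0% is about 55% as specified, and at most 68% two-sided if attrition is ignored. On its stated inputs the 960-patient design did not have 80% power for a risk ratio of 1.4, so describing it as conservatively powered for that effect is wrong. The 79.0% at N=720 should be about 64% to 74%. At N=640 the effective sample size should be about 690, giving about 65% and 77% instead of 70% and 81%.

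The 85.0% result rests on a two-sided 0.05 test and the attrition stated. The repeated-measures results also assume the same rates at both visits and the plan's correlation of 0.6. It does not follow that the reductions had no other basis, or that the effects the finished trial can exclude have changed: those will depend on its confidence intervals.

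**What to change.** Change the text of section VI as follows.

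1. Replace 85.0% with about 55%, and delete the statement that the study was initially powered conservatively for a risk ratio of 1.4.
2. Replace the effective sample size of 768 with about 690, and restate 70% and 81% as about 65% and 77%.
3. Restate the 79.0% with the 3-month attrition it assumes; it will fall between about 64% and 74%.
4. Keep 96.8%, but say that it refers to 15% vs 24% with attrition only by month 6.
5. Print the sample size and attrition that the power table uses.

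Recruitment, randomisation and analysis are unaffected. The cost is a text amendment and less favourable stated power.
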